2.10. Rationale of study

When it comes to surveillance of Barrett's oesophagus, there is a need to enhance the clinical pathway and streamline the use of resources. There is also a reason to evaluate and introduce alternative surveillance methods that are better tolerated by patients. Cell collection device with sponge can be one such method, EndoSign® has not yet been used in Swedish healthcare and the method therefore needs to be evaluated in our setting. The similar cell collection device Cytosponge have been used as a triage tool, patients under surveillance could be divided into various risk groups. This might direct medical interventions toward people who are most at risk of developing cancer. In the future, Cell

Clinical Investigation Plan
Study Code: ES-100
CIV-ID: CIV-23-06-043373

collection device with sponge might be used to screen patients with gastroesophageal reflux disease (GERD) for Barrett's oesophagus.

In order to be able to conduct high-quality research on Barrett's oesophagus, a sufficiently large patient base is needed. Both regional and county hospitals conduct surveillance, so it would be advantageous if they all collaborated in future research on Barrett's oesophagus in Sweden.

With this feasibility study, it is possible to introduce and assess EndoSign® within the Swedish Barrett network at a number of hospitals in a controlled manner, which can serve as a crucial foundation for carrying out larger multi-center studies in the future.

3. Risks and clinical benefits of the investigational device and clinical investigation

3.1. Expected clinical benefits

Early detection of oesophageal cancer is the single most important factor in improving the outcome of treatment. This is made possible by identifying patients at risk of developing oesophageal cancer and following these in a surveillance protocol.

Today, no screening is being conducted for Barrett's oesophagus but this is debated. ESGE guidelines recommend screening of high-risk patients. Cell collection device on a sponge, such as Cytosponge-TFF3, has shown promising results in targeted screening of Barrett's oesophagus in patients with GERD.

Surveillance of Barrett's is conducted with repeated endoscopies where the quality depends on the experience and skill of the endoscopist. There are studies that have shown that endoscopists to varying extent fail to adhere to recommended guidelines regarding e.g. how biopsies should be taken.

The availability of endoscopy differs between hospitals and has been generally limited during the COVID-19 pandemic. Surveillance is costly and with the implementation of cell collection device with sponge it could be possible to re-design clinical pathways and reduce the number of endoscopies needed, which would also increase availability. Most patients will not develop cancer and it would be desirable to prioritize endoscopy resources to the patients who benefit the most.

Cytosponge-TFF3 has been used as a triage to prioritize patients to endoscopy.[13] There is a need to study and validate whether the use of sponge devices coupled with TFF3-analysis in surveillance can improve surveillance, reduce resource utilization and improve outcomes in patients. This feasibility study is an important first step in order to be able to conduct larger studies in the future.

Clinical Investigation Plan
Study Code: ES-100
CIV-ID: CIV-23-06-043373

TFF3- analyses of the cell materials from the sponge is performed by Cyted laboratory in the UK and there is reason to evaluate how the logistics of this work.

3.2. Anticipated adverse device effects

Potential complications include: Mucosal laceration or perforation requiring secondary intervention, Bleeding, Aspiration, Intestinal obstruction, Tissue damage, Dysphagia, Pain, Sore throat., Dyspepsia indigestion reflux, Oesophageal or gastric pain, Nausea or vomiting, Voice disturbance, Diarrhoea or an upset stomach, Chest pain or discomfort, Vasovagal attack. Headache, Hernia, Detachment of the sponge.

3.3. Risks associated with participation in the clinical investigation

Participation in the clinical investigations means that the subject will undergo at least one EndoSign® test and a gastroscopy, which entails (albeit a small) risk of complications.

3.4. Steps to be taken to control or mitigate risks

The clinical investigation is conducted in hospitals, which are well-equipped to handle any complications or unexpected results. Healthcare professionals leading the study sessions are knowledgeable about the research project and the treatments being used.

3.5. Rationale for benefit-risk ratio

The advantages for the individual subject are an in-depth investigation (in addition to surveillance) of Barrett's esophagus where the EndoSign® coupled with TFF3-analysis can detect atypia, dysplasia and early cancer.

In the long term, this and future studies can potentially improve the quality of surveillance and treatment of Barrett's esophagus.

4. Objectives and hypotheses of the clinical investigation

4.1. The purpose of the clinical investigation

- To determine whether it is feasible to use EndoSign® with TFF3 analysis coupled with p53 and atypia in patients with Barrett's oesophagus under surveillance
- Acquire data and experience to assess whether it is possible to perform a full scale study in the future and identify what design modifications are needed
- Determine steps necessary for implementation in secondary care.

Clinical Investigation Plan
 Study Code: ES-100
 CIV-ID: CIV-23-06-043373

4.2. Objectives and endpoints

Objective	Endpoint	
To assess patient acceptability for EndoSign®	i. EndoSign® test experience compared to upper GI endoscopy ii. EndoSign® swallowing failures iii. Willingness to undergo EndoSign® again	i. Adapted ENDOPREM and a visual analog scale to rate experience ii. Number of patients that are unable to swallow and attempts made iii. Questionnaire
To assess safety of EndoSign® in secondary care	i. Rates of adverse events up to 7 days after EndoSign® test	i. All adverse events reported during procedure, ER-visits and 7-day follow up.
To assess the feasibility of recruitment	i. Proportion of eligible patients who participate ii. Quantify the number of patients that potentially can be recruited	i. Patients accepting invite and consent divided by total of patients invited ii. Number of patients in surveillance per site
To assess the implementation of EndoSign®	i. Costs and resources required to introduce EndoSign® in secondary care ii. Determine technology and equipment needs and training iii. Clinical staff experience and acceptability of EndoSign® in regards of training, skills, reliability, side effects and user information	i. Interviews with staff and healthcare professionals ii. Equipment needed per session iii. Number of sessions needed until fully trained. iii. Interview with clinical staff iv. Number of days from samples are sent to laboratory in UK until test results arrive

Clinical Investigation Plan
 Study Code: ES-100
 CIV-ID: CIV-23-06-043373

	iv. Logistics of TFF3-analysis of EndoSign® and response times	
To evaluate data collection method and outcome measures	i. Feasibility of questionnaires ii. Response rate for questionnaires iii. Withdrawal and drop-out rates iv. Follow-up rates	i. Validate adapted ENDOPREM ii. The proportion of patients who completes each questionnaire iii. The proportion of patients who, for various reasons, do not complete the study iv. The proportion of patients who complete the follow-up
Preliminary evaluation of results and patient outcomes	i. Demographics of the patient group ii. Patient reported outcome, questionnaire iii. EndoSign® -TFF3 test results (atypia, p53 status, TFF3 status) iv. Number of inadequate samples v. Classification of patients into different risk groups and show preliminary results when used as triage method vi. Results from endoscopy and biopsies and compare to EndoSign® test results	i. Data collected and reported in the CRF collected at first visit ii. VAS, adapted ENDOPREM, EQ-5D iii. Proportion of patients with adequate sampling with positive test iv. Reason for not generating result v. Number of patients categorizes into low, moderate and high risk according to p53 and atypia, combined with clinical factors age, sex, length of segment. vi. Length of BE-segment, visible lesion, intestinal metaplasia, low-grade dysplasia, high grade dysplasia

Clinical Investigation Plan
Study Code: ES-100
CIV-ID: CIV-23-06-043373

5. Design of the clinical investigation

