5.5. Description of the clinical procedures and diagnostic methods relating to the clinical investigation

EndoSign® test procedure

Study patients are referred to a separate visit to undergo the EndoSign® test. They will be required to refrain from food and liquids for 3–4 hours before the visit and they will respond to a socio-demographic- and clinical form and assessment of symptoms and EQ-5D.

Clinical Investigation Plan
Study Code: ES-100
CIV-ID: CIV-23-06-043373

The EndoSign® is administered by a nurse or healthcare professional that has undergone adequate procedure training. The procedure time is 7 minutes with an overall clinic session taking about 20- 30minutes in total.

The patient is asked to swallow the EndoSign® capsule together with some water. The end of the suture is attached to an applicator which the nurse hands to the patient to hold. The capsule will be in the patient's stomach for around 7minutes until it dissolves completely, allowing the sponge to expand to its full size. The sponge is withdrawn by the nurse using the suture. The patient can choose to get local anaesthetic spray into their throat before the sponge is removed. The sponge is then placed in a sample collection kit provided by Cyted and secured with a patient number identification label.

The patient will be instructed to try again if they are unable to swallow the capsule the first time. Before being labelled as "EndoSign® swallowing failure," patients will have a maximum of two failed attempts.

After 30 minutes, patients are asked to answer forms about anxiety level and procedure-specific questions to evaluate acceptability. The visual analog scale (VAS) and a quick questionnaire using the adapted ENDOPREM measure will be used.

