8.1 Case Report Form

All data will be anonymized and stored in an electronic study database (e-CRF) using REDCap. The following data will be collected and reported directly in the CRF:

- Sex, age, BMI
- Smoking / Alcohol consumption
- Use of PPI or other acid suppressants
- Year of diagnosis
- Prague classification according to previous endoscopy
- Previous dysplasia
- Previous endoscopic treatments
- Patient-reported experience measurement data (ENDOPREM, VAS)
- Questionnaire results (including EQ-5D)
- EndoSign® -TFF3 test results
- Gastroscopy results (including biopsy results)
- Adverse events

Both written and electronic changes or corrections on CRF will be dated, initialed and explained (if necessary)

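### The cost part of implementation endpoint i, and staff time, rest on staff interviews alone; no price or staff-time variable is planned

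*Protocol*

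**What the plan says.** The objectives table in protocol section 4.2 lists four endpoints for the implementation of EndoSign. The first is "Costs and resources required to introduce EndoSign® in secondary care". The measure carrying the same numeral is "Interviews with staff and healthcare professionals".

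The second endpoint is "Determine technology and equipment needs and training", and the measure column continues with counts: "i. Interviews with staff and healthcare professionals ii. Equipment needed per session iii. Number of sessions needed until fully trained". The fourth endpoint, laboratory logistics, is measured as "Number of days from samples are sent to laboratory in UK until test results arrive".

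Cost is part of the case for the study. Section 3.1 says "Surveillance is costly and with the implementation of cell collection device with sponge it could be possible to re-design clinical pathways" and goes on to name resource use as something that sponge testing still has to be studied for. Section 4.1 gives the steps needed for implementation in secondary care as one of three purposes. It sets no cost-effectiveness aim and no cost threshold.

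The only statement about staff time per test is in section 5.5, under the test procedure: a procedure time of 7 minutes, with an "overall clinic session taking about 20- 30minutes in total". This is a description of the visit. It is not listed as something to be measured.

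**The concern.** An endpoint that names costs needs a data source that can produce a cost: resource items, units, and a price for each. For endpoint i the protocol names the respondents and stops there. If the interviews turn to effort and practical difficulty, the sponsor will know how introduction felt to the staff but will have no recorded minutes and no prices to set beside the counts of equipment, training sessions and turnaround.

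The two missing pieces differ in urgency. Prices for the device, kit, laboratory work, transport and training should exist in invoices or price lists and can be collected late. Staff time is observable only while a session is running. Asked for afterwards, it comes back as a rounded recollection over a whole series of patients. An analysis plan written later cannot supply minutes that no form recorded, so this is a matter for the protocol rather than for the SAP.

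**Working it through.** The protocol gives no cost figure to reproduce, so the check sets each implementation endpoint in section 4.2 beside its measure and then looks for cost data elsewhere.

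| Endpoint (4.2) | Measure (4.2) | Kind |
|---|---|---|
| i. Costs and resources | Interviews | Interview |
| ii. Technology, equipment, training | Equipment per session; training sessions needed (numbered iii in the measure column, but it fits endpoint ii) | Two counts |
| iii. Staff experience and acceptability | Interviews | Interview |
| iv. Laboratory logistics | Days from dispatch to result | One count |

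The objective as a whole therefore has three counted measures and two interview measures. Endpoint i has one measure, an interview, and no cost variable.

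**Search elsewhere in the protocol**

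- Section 8.1 opens its list with "The following data will be collected and reported directly in the CRF". Of the 12 bullets that follow, none is a price, a staff time or a resource item.
- Table 1 (flow chart) has no such row.
- Section 5.5 describes session length but does not ask for it to be recorded.
- Section 7 (statistical considerations) does not mention cost.
- Section 11 logs device quantities and dates of use for each subject, without price or time.

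**Inputs for a cost per test that are already recorded**

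- Swallowing failures and attempts (4.2, acceptability).
- Inadequate samples and their reasons (4.2, preliminary evaluation).
- Devices used (section 11).

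The pieces with no planned source other than interviews are unit prices and staff time.

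**Scale, for illustration only**

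- Staff time. Inputs: 75 tests (5.1) and 20 to 30 minutes per session (5.5). 75 × 20 / 60 = 25 hours; 75 × 30 / 60 = 37.5 hours. The upper figure is 37.5 / 25 = 1.5 times the lower, for one staff member per session.
- Cost per adequate result relative to cost per attempted test is 1 / (1 − f), where f is the share of attempted tests that give no result. The protocol gives no f for this device. Assumed values: f = 5% gives 1 / 0.95 = 1.05; f = 10% gives 1 / 0.90 = 1.11; f = 20% gives 1 / 0.80 = 1.25.
- Training. Section 2.8 says that sign-off usually takes 8 to 10 procedures; each site has 15 patients. 8 / 15 = 53% and 10 / 15 = 67%. One trainee's procedures thus equal more than half of a site's study sessions, so training may be a sizeable part of introduction cost. The sessions will be counted, but their duration and price will not be recorded.

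**The case against.** **Interviews are not confined to opinion.** They can ask for minutes, quantities and prices, and the interview guide is not part of the document at hand. This stands. A reader might infer that the trial will end with opinions and no cost figure, but the protocol does not say so. What it does show is that no item, unit or price source is fixed, and that time would be recalled rather than recorded.

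**Resources are not left to interviews alone.** Equipment, training sessions and turnaround are all counted under this objective. This also stands, and it limits the point to cost and staff time.

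**Absence from section 8.1 and Table 1 proves little.** Both are about patients, and the three counted implementation measures are missing from them too. That is fair. The point rests on the absence of any planned price or staff-time item in the whole document, not on the case report form list.

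**The endpoint concerns what introduction requires, and no cost-effectiveness aim is stated.** A cost per test would not settle whether redesigned pathways save money. That is correct, and it keeps the point small. It does not remove it, because cost of introduction is itself a declared endpoint.

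**Conclusion.** The point holds in a limited form. For endpoint i the protocol names interviews as the only data source, and no section plans to record prices or staff time. The cost part of the endpoint therefore has no defined item, unit or price source.

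A reader might go further and conclude that the implementation objective, or the planning of a full-scale study, is left unanswered. The document does not support that. Endpoints ii to iv keep their measures, three of the quantities involved are counted, and failures and inadequate samples are already recorded.

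The 25 to 37.5 hours and the ratios of 1.05 to 1.25 show what a cost figure would depend on. They do not measure an error caused by interviewing. The ratios rest on assumed failure shares, and the hours on one staff member per session. The conclusion itself rests on the protocol alone; an interview guide with structured costing questions would narrow the gap, though it would still rely on recall for time.

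This is a cheap improvement. It does not affect the sample size.

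**What to change.** Extend the measure for implementation endpoint i in section 4.2 with two items:

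- (a) unit prices, from existing invoices or price lists, for device and kit, laboratory analysis, transport to the UK and training;
- (b) a one-line log for each EndoSign session, training sessions included, with start time, stop time and staff category.

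State that introduction cost will be reported per site, together with mean cost per attempted test and per adequate result, using the swallowing failures and inadequate samples already recorded. Keep the interviews for qualitative resource needs. If the sponsor prefers not to collect these data, reword endpoint i so that it covers perceived resource needs only.

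Cost: about 75 log lines for the study tests, plus the training sessions. With 75 / 15 = 5 sites, one trainee per site and all training procedures outside the 75 (assumptions), that adds 5 × 8 = 40 to 5 × 10 = 50 lines, or 115 to 125 in total. Each further trainee adds 8 to 10. Existing invoices have to be gathered and the wording of section 4.2 changed. There is no added burden on patients. The log has to be in place before sessions start; the prices can follow.

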5.1. General information

This clinical investigation is designed as a single-armed multi-center feasibility study and is expected to be conducted 2023/2024. The aim is to include 15 consecutive patients per site (75 patients in total) attending routine endoscopy in Barrett's esophagus surveillance.

5.3. Study timetable

Estimated subject enrollment start Dec 1st 2023

Estimated last enrollment: April 1st 2024

Last follow up: Oct 31st 2024

5.4. Subjects

Inclusion criteria

- Patients with histopathologically confirmed diagnosis (intestinal metaplasia) of Barrett's oesophagus (BE) and at least C0M1
- Active monitoring with planned surveillance endoscopy within 3 to 12 months
- Age 18 – 84 years

Exclusion criteria (any of the following)

- Scheduled for other endoscopic treatment (e.g. ablation) at the next surveillance endoscopy
- Alarm symptoms
 - Dysphagia and/or food sticking
 - Dyspepsia and weight loss
 - Dyspepsia and anaemia
- Patient with a diagnosis of an oropharyngeal, oesophageal, or gastro-oesophageal tumour

Clinical Investigation Plan
Study Code: ES-100
CIV-ID: CIV-23-06-043373

- Patient who has had treatment to the oesophagus e.g. endoscopic mucosal resection, endoscopic submucosal dissection, radio frequency ablation, surgery within the previous two months
- Patient known to have oesophageal varices or cirrhosis of the liver
- Patient with a known anomaly of the oesophagus e.g. webbing, pouch, stricture etc.
- Patients unable to give consent
- Patients who have had a stroke or any other neurological disorder where their swallowing has been affected
- Patients who have had a myocardial infarction in the last 3 months
- Patients who have had fundoplication or other surgery to oesophagus and proximal stomach
- Patients using anti-trombotic drugs which cannot be temporarily discontinued

Investigation population

5.4.3. 75 (15 patients per site)

5.4.4. Criteria and procedures for subject withdrawal or discontinuation.

All study participants may discontinue their participation in the study at any time without this affecting their continued surveillance and future treatments. Collected data for the patient will be retained or destroyed depending on the patient's desire

5.4.5.

Subject enrolment

A nurse or physician identifies eligible patients to undergo a gastroscopy as part of Barrett's oesophagus surveillance. These patients are asked for participation in the study via an invitation letter or telephone call. Interested patients will be provided with written information about the study and EndoSign® information leaflet. If the patient chooses to participate, written informed consent will be obtained and stored locally. Each secondary care clinic will maintain an anonymized screening log that

5.5.1. lists all screened patients. Recruitment continues until 75 patients are included.

5.5. Description of the clinical procedures and diagnostic methods relating to the clinical investigation

EndoSign® test procedure

Study patients are referred to a separate visit to undergo the EndoSign® test. They will be required to refrain from food and liquids for 3–4 hours before the visit and they will respond to a socio-demographic- and clinical form and assessment of symptoms and EQ-5D.

Clinical Investigation Plan
Study Code: ES-100
CIV-ID: CIV-23-06-043373

The EndoSign® is administered by a nurse or healthcare professional that has undergone adequate procedure training. The procedure time is 7 minutes with an overall clinic session taking about 20- 30minutes in total.

The patient is asked to swallow the EndoSign® capsule together with some water. The end of the suture is attached to an applicator which the nurse hands to the patient to hold. The capsule will be in the patient's stomach for around 7minutes until it dissolves completely, allowing the sponge to expand to its full size. The sponge is withdrawn by the nurse using the suture. The patient can choose to get local anaesthetic spray into their throat before the sponge is removed. The sponge is then placed in a sample collection kit provided by Cyted and secured with a patient number identification label.

The patient will be instructed to try again if they are unable to swallow the capsule the first time. Before being labelled as "EndoSign® swallowing failure," patients will have a maximum of two failed attempts.

After 30 minutes, patients are asked to answer forms about anxiety level and procedure-specific questions to evaluate acceptability. The visual analog scale (VAS) and a quick questionnaire using the adapted ENDOPREM measure will be used.

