ITT	Intention-to-treat = including all data from all subjects who have participated in the clinical investigation
MDCG	Medical Device Coordination Group
PMCF	Post-Market Clinical Follow Up
PP	Per Protocol analysis = including only data from subjects who have completed the clinical investigation completely in accordance with the CIP, with no deviations from the CIP
RFA	Radiofrequency ablation
SADE	Serious Adverse Device Effect
SAE	Serious Adverse Event
USADE	Unanticipated Serious Adverse Device Effect
VAS	Visual analog scale

Clinical Investigation Plan
 Study Code: ES-100
 CIV-ID: CIV-23-06-043373

1. Synopsis

Background and rationale:	
Investigational device:	EndoSign® Cell collection device
Number of subjects:	75 (15 per site)
Inclusion criteria:	
 ● Patients with histopathologically confirmed diagnosis (intestinal metaplasia) of Barrett's oesophagus (BE) and at least COM1 ● Active monitoring with planned surveillance endoscopy within 3 to 12 months ● Age: 18 – 84 years
Exclusion criteria:	
 ● Scheduled for other endoscopic treatment (e.g. ablation) at the next surveillance endoscopy ● Alarm symptoms 
 ○ Dysphagia and/or food sticking ○ Dyspepsia and weight loss ○ Dyspepsia and anaemia ● Patient with a diagnosis of an oropharyngeal, oesophageal or gastro-oesophageal tumour ● Patient who has had treatment to the oesophagus e.g. endoscopic mucosal resection, endoscopic submucosal dissection, radio frequency ablation, surgery within the previous two months ● Patient known to have gastric or oesophageal varices or cirrhosis of the liver ● Patient with a known anomaly of the oesophagus e.g. webbing, pouch, stricture etc ● Patients unable to give consent ● Patients who have had a stroke or any other neurological disorder where their swallowing has been affected ● Patients who have had a myocardial infarction in the last 3 months ● Patients who have had fundoplication or other surgery to oesophagus and proximal stomach ● Patients using anti-trombotic drugs which cannot be temporarily discontinued

Clinical Investigation Plan
 Study Code: ES-100
 CIV-ID: CIV-23-06-043373

[figure not shown]

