14.3 List of foreseeable Adverse events

Foreseeable adverse events*	Incidence (%)	Mitigation and treatment
Adverse events		
Sore throat	44	Conservative treatment, analgesics
Dyspepsia indigestion reflux	13	Conservative treatment, acid suppressants
Oesophageal or gastric pain	11	Conservative treatment, analgesics

Version No: 1.1

Date: 2023-11-29

Clinical Investigation Plan

Study Code: ES-100

CIV-ID: CIV-23-06-043373

Feeling non-specifically unwell	6	Conservative treatment
Nausea or vomiting	6	Conservative treatment, antiemetics
Voice disturbance	3	Conservative treatment
Diarrhea or an upset stomach	4	
Chest pain or discomfort	1	Conservative treatment, analgesics
Allergic reaction	1	Conservative treatment, allergy treatment
Anxiety	1	Conservative treatment
Bad taste	1	Conservative treatment
Paroxysmal positional vertigo	1	Conservative treatment
Blood clot excretion	1	Conservative treatment
Vasovagal attack	1	Conservative treatment
Nosebleed	1	Conservative treatment
Headache	1	Conservative treatment, analgesics
Bloodshot eye	1	Conservative treatment
Chest infection	1	Conservative treatment, antibiotics
Abrasion	1	Conservative treatment
Fall	1	Conservative treatment, orthopedic consultation
Serious adverse event		
Detachment of the sponge on day of the procedure	1	Endoscopy
Hernia	1	Surgery
Myocardial infarction	1	Cardiological treatment
Perforation	N/A	Endoscopic or surgical intervention, conservative treatment, antibiotics
Serious bleeding	N/A	Endoscopic or surgical intervention, blood transfusions

15 Premature termination of the clinical investigation

The sponsor may suspend or prematurely terminate either the clinical investigation at an individual investigation site or the entire clinical investigation for significant and documented reasons. The Swedish Medical Products Agency may suspend or prematurely terminate the clinical investigation at the applicable investigation sites.

If suspicion of an unacceptable risk to subjects arises during the clinical investigation, or when so instructed by the Medical Products Agency, the sponsor will suspend the clinical investigation while the risk is assessed. The sponsor will terminate the clinical investigation if an unacceptable risk is confirmed. The sponsor will inform all investigators.

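### Known gastric varices exclude a patient in the synopsis but not in section 5.4

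*Protocol*

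**What the plan says.** Exclusion criteria appear in two places in the current protocol (version 1.1).

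- **Section 1, Synopsis:** "Patient known to have gastric or oesophageal varices or cirrhosis of the liver".
- **Section 5.4, Subjects:** "Patient known to have oesophageal varices or cirrhosis of the liver".

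The list in 5.4 is headed "Exclusion criteria (any of the following"), so meeting one item is enough to exclude. It does not refer back to the synopsis. The text shown does not mention varices anywhere else.

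Three other places bear on why the criterion matters:

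- The test procedure in section 5.5: "The capsule will be in the patient's stomach for around 7minutes until it dissolves completely, allowing the sponge to expand to its full size". The nurse then withdraws the sponge by its thread.
- Section 3.2, whose list of potential complications includes "Mucosal laceration or perforation requiring secondary intervention, Bleeding".
- Section 14.3, which lists serious bleeding as a foreseeable serious adverse event with incidence N/A. Its management is given as "Endoscopic or surgical intervention, blood transfusions".

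**The concern.** An exclusion criterion is an operative instruction: it decides who may swallow the device. Here the same protocol gives two answers for one type of patient, and the section that a site would naturally use for screening carries the less protective one.

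Three things are at stake.

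- **Safety.** The stomach is where the sponge expands and where its withdrawal begins, so gastric varices lie in the region the device passes through. That they raise the bleeding risk is a clinical inference. The protocol does not state it, although the synopsis wording suggests that the sponsor had it in mind.
- **Conduct.** Section 10 forbids deviations except to protect subjects in an emergency, and section 6.11 has a monitor check compliance with the plan. With two criteria in force, a monitor cannot say whether enrolling such a patient is a deviation. With 15 patients at each of five sites, different staff may work from different lists.
- **Analysis set.** The abbreviation list defines per protocol as no deviations from the plan. The per-protocol status of such a patient is therefore undefined.

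**Working it through.** There is no figure to reproduce, so the check is a comparison of texts.

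**Step 1: count and match the criteria.** Both lists have 11 top-level exclusion criteria, in the same order.

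| No. | Subject of criterion | Synopsis vs 5.4 |
|---|---|---|
| 1 | Other endoscopic treatment scheduled | same |
| 2 | Alarm symptoms (three sub-items) | same |
| 3 | Tumour diagnosis | same |
| 4 | Oesophageal treatment in the previous two months | same |
| 5 | Varices or cirrhosis | **differs: gastric varices only in synopsis** |
| 6 | Oesophageal anomaly | same |
| 7 | Unable to consent | same |
| 8 | Stroke or neurological disorder affecting swallowing | same |
| 9 | Recent myocardial infarction | same |
| 10 | Fundoplication or other surgery | same |
| 11 | Anti-thrombotic drugs that cannot be stopped | same |

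Ten of 11 match apart from punctuation, and 11 − 10 = 1 differs in substance. Both versions of criterion 5 are complete sentences with no gap, so neither redaction nor PDF extraction is a likely explanation. Both stand in the current text and not in a log of changes.

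**Step 2: look for another 5.4 criterion that closes the gap.** The nearest is "Patient with a known anomaly of the oesophagus e.g. webbing, pouch, stricture etc", which is limited to the oesophagus. The surgery criterion concerns past operations. The alarm-symptom criterion would catch such a patient only incidentally, for example if dyspepsia and anaemia were also present. None is aimed at gastric varices.

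**Step 3: identify who is affected.**

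| Known condition | Synopsis | Section 5.4 |
|---|---|---|
| Cirrhosis | excluded | excluded |
| Oesophageal varices | excluded | excluded |
| Gastric varices, without either of the above | excluded | **eligible** (if no other criterion applies) |

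Only the last row is in conflict.

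**Step 4: look for a rule of precedence.** The text shown contains none.

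**Step 5: size.** The protocol gives no prevalence of isolated gastric varices and no incidence of serious bleeding, so an effect on event rates cannot be calculated. If 0 to 1 of the 75 planned patients is affected, the share is 0/75 = 0% to 1/75 = 1.3%. That range is an assumption without support in the document and serves only to show that the group is small.

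**The case against.** The best case on the other side accepts the mismatch and disputes its weight.

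- **Reach.** Cirrhosis and known oesophageal varices exclude under both lists. What remains is a patient in active Barrett's surveillance with known gastric varices and neither of those conditions. Nothing shows that any site has one. This stands, and it is why the point is minor.
- **An unseen safeguard.** Sections 2.6 and 2.7 refer to Appendix A, the instructions for use, whose text is not shown. A contraindication there would remove most of the safety consequence. This also stands as a limit, but the two lists in the plan would still disagree.
- **An inferred harm.** The protocol lists bleeding as a general complication and does not tie it to gastric varices. That is correct, so the bleeding argument is plausible but not quantified.
- **Which wording is right.** The document does not prove that 5.4 lost two words; the synopsis could be the outdated text. With the other ten criteria nearly identical, a dropped phrase is the likelier explanation, and the synopsis wording is the safer choice. The sponsor should still confirm its intent.
- **No scientific effect.** This is a single-arm feasibility study without a power calculation. The mismatch changes no endpoint, analysis or sample size. True, but eligibility has to be unambiguous whether or not it affects an estimate.

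None of these points reconciles the two texts.

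**Conclusion.** The inconsistency is real. One of 11 exclusion criteria differs in substance between the synopsis and section 5.4, and the wording in 5.4 would admit a patient whom the synopsis bars. Severity is minor: the affected group is narrow, and no sample size, endpoint or analysis depends on it.

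The contradiction rests on the text alone and needs no assumption. The safety argument rests on the clinical inference that gastric varices add bleeding risk with this device, and it depends on what Appendix A says. The same limit applies to the few other protocol pages not available for review, where a rule of precedence could stand.

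**What to change.** Add the words *gastric or* before *oesophageal varices* in the section 5.4 criterion, so that it matches the synopsis, after the sponsor has confirmed that this is what was meant. Use the same wording in any screening form, and check it against the instructions for use in Appendix A.

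The cost is two words in the protocol and whatever procedure section 9 requires for an amendment. The criterion concerns *known* varices, so no extra test is needed. On the assumption above, at most about one of the 75 patients would be lost to recruitment.
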